#### Blood sample processing:

The blood from the heparinised tubes will be spun and separated in the laboratory to provide plasma, peripheral blood mononuclear cells (PBMCs) and DNA isolation.

Samples will be used directly for immune analysis, or stored in freezers at -80°C and -135°C respectively, until further testing.

**Table 3** describes the different assays, which are planned

#### Mucosal sample processing:

Freshly collected MLF samples will be used directly for immune analysis, or processed and stored in freezers at -20°C/-80°C, until further testing.

#### 12.3 Sample storage

To ensure uniform handling and processing of samples the ones that can be frozen without loss of quality will be stored in the PERISCOPE biobank, which is located at the Radboud University Medical Centre, Nijmegen, the Netherlands. This includes storage for short periods of samples that will be analysed at labs other than where the samples were obtained and material left over after analyses are done. The labs where the analyses will be done during the PERISCOPE project are all part of the PERISCOPE consortium. The PERISCOPE biobank also includes storage of left over samples for maximally 10 years after the end of the PERISCOPE project. Any samples from the Biobank will only be used for the study purposes and objectives of the PERISCOPE project. This includes samples that are left after the duration of the project, as we anticipate analysis of samples during the project are described in the research proposal. Samples that are left over after the project will only be used to answer the research questions of the PERISCOPE project. To ensure this, we will install a group of senior PI's of PERISCOPE to oversee and decide on the use of the samples after PERISCOPE has ended.

The Radboud university medical center is listed in the Commercial Register of the Chamber of Commerce under file number 41055629.

#### 12.4 Laboratory tests (primary objective)

#### Analysis of Serum/plasma antibody responses

The concentration of PT, other pertussis specific antibodies and antibodies relating to the nonpertussis vaccine antigens will be measured from plasma using a flow-cytometric based method with antigen-coated fluorescent beads (BioPlex/Luminex) at the National Institute for Public Health and the Environment – RIVM, Centre for Infectious Disease Control (Clb), [name], the Netherlands. In the fluorescent-bead-based multiplex immunoassay (MIA), each antigen of interest is coupled to beads with a distinct fluorescence. Combination of these beads enables the detection of antibodies directed against multiple antigens in one single serum sample, using Luminex technology. IgG-PT antibody concentrations as primary outcome will be measured in duplicate in two dilutions using an in-house standard, calibrated on the WHO reference serum for pertussis as standard expressed in IU/mI.

Using different conjugates, IgG-total, IgG-subclasses and -avidity, and IgA-specific antibody concentrations can be measured in serum with the MIA. Besides anti-pertussis specific antibody concentrations, the other vaccine-specific IgG-antibody concentrations of diphtheria and tetanus will be measured with MIA in two dilutions using the national reference serum (IU/mI) as standard, which has been calibrated against the WHO standard [59-61].

## 12.5 Other laboratory tests (secondary and exploratory objectives)

## Analysis of B-cell and T-cell responses (secondary and exploratory objectives)

One of the most studied potential correlates of protection in pertussis are serum antibodies. There is also evidence that B and T cells can have a relevant role. Studies have shown that the type of vaccine used in priming (aP vs wP) can effect the response of B and T cells to the booster vaccination [33, 62].

The rationale for this analysis is to increase our knowledge in how antigen specific B and T cells can be induced and maintained after different priming immunisation schedules (aP vs wP).

Memory B cell responses to Bp will be analysed by enzyme-linked immunospot assay (ELISpot) following B-cell culture with polyclonal stimulants. The ELISpot is a sensitive immunoassay to enumerate antigen specific antibody-secreting cells (ASCs). This assay will be undertaken using PBMCs that have previously been frozen following collection.

T-cell responses to Bp will be performed to determine the quantity, quality and persistence of antigen-specific T cell responses in the blood, allowing a comparison of cellular immunity in different groups of participants. This may involve a whole-blood stimulation assay which will be used and undertaken in the laboratory on fresh blood. Whole blood/PBMCs will be stimulated with antigens according to a protocol developed as part of the PERISCOPE consortium. The stimulated cells and supernatants will then be frozen pending subsequent transfer to collaborators in the PERISCOPE consortium for analysis by flow-cytometry and cytokine detection in supernatants.

#### Functional antibody responses

To better understand the functionality of pertussis vaccine-induced antibodies, that have a relevant role in protection against the disease, a variety of assays will be used in this study. The assays, as

an essential part of the PERISCOPE consortium, will be established as core standardised immunoassays. Although not limited to these assays alone, the *in vitro* assays may include: 1) adherence inhibition, to measure the ability of antibodies to inhibit the adherence of Bp to respiratory epithelial cells; 2) bacterial agglutination, to measure the ability of the antibodies to induce bacterial aggregation 3) pertussis toxin neutralization 4) opsonisation and 5) phagocytosis, to measure the uptake and killing by phagocytic cells.

#### Dynamics of the immune response to pertussis vaccination

Analysis of the genomic variation (SNP's candidates, B cell repertoire); epigenetic variation (methylation and histone modification) may be undertaken as part of exploratory analyses and linked to measure of Bcell and T cell response to better understand variation between individuals.

#### Analysis of mucosal antibody and/ or cytokine responses

The concentration of PT and other pertussis specific antibodies against vaccine antigens, as well as the concentration of T cell cytokines (e.g. IL17, IFNg and IL4/5/13), will be measured in mucosal samples, obtained from MLF. This will allow us to determine the induction and persistence of those antibodies and / or cytokines before (2 months) and after vaccination (5 and 12 months). Cytokine concentrations will be determined using methods such as Luminex. The determination of antibody responses will be determined using similar methods to serum and plasma samples (MIA, Bacterial adherence inhibition assay (BAI) and Serum bactericidal antibodies assays (SBA)).

## **13.SAFETY REPORTING**

#### **13.1 Premature termination or suspension of a trial**

In accordance to sections 5.16 and 5.21 of the international committee on harmonisation (ICH) guidance on good clinical practice (GCP), the sponsor will suspend the study if there are sufficient grounds to believe that continuation of the study will jeopardise subject health or safety. The sponsor will notify the accredited research ethics committee (REC) and competent authority (CA), according to local requirements. The study will be suspended pending a further positive decision by the accredited MREC. The investigator will take care that all subjects are kept informed.

Nevertheless, the local sponsor is entitled to terminate the study prematurely if this is beneficial to the health or welfare of the subjects and after advice from the DSMC.

The REC and CA will be informed about such a decision, according to local requirements.

In case of premature study termination, there will be no consequences for a participant other than that further blood sampling is suspended and any ongoing SAEs will be followed up.

# 13.2 Adverse events, serious adverse events and suspected unexpected serious adverse reactions - Definitions

#### 13.2.1 Adverse events (AE)

#### a) Definition:

An AE or adverse event is:

Any untoward medical occurrence in a patient or clinical investigation participant administered a medicinal product, which does not necessarily have to have a causal relationship with this treatment (the study medication).

An AE can therefore be any unfavourable and unintended sign (including an abnormal laboratory finding), symptom or disease temporally associated with the use of the study medication, whether or not considered related to the study medication.

## 13.2.2 Serious adverse events (SAE)

## a) Definition:

A SAE is any untoward medical occurrence or affect that at any dose:

-results in death;

-is life threatening (at the time of the event);

-requires hospitalisation or prolongation of existing inpatients' hospitalisation;

-results in persistent or significant disability or incapacity;

-is a congenital anomaly or birth defect; or

-any other important medical event that did not result in any of the outcomes listed above due to medical or surgical intervention but could have been, based upon appropriate judgement by the investigator.

A hospital admission for an elective procedure will not be considered as a SAE.

Other 'important medical events' may also be considered serious if they jeopardise the participant or require an intervention to prevent one of the above consequences. For this specific case, hypotonic hyporesponsive episodes, even if they do not require hospitalisation, would be considered a medically relevant event and reported as an SAE if occuring within 48hours after immunisation. Although this event is considered rare it has been described to occur more commonly after wP vaccination compared to aP. Pertussis confirmed cases would be reported as an SAE, due to a reduced primary schedule (2+1) when compared with the current UK schedule (3+0).

NOTE: The term "life-threatening" in the definition of "serious" refers to an event in which the participant was at risk of death at the time of the event; it does not refer to an event, which hypothetically might have caused death if it were more severe.

## 13.2.3 Adverse Reactions (AR)/ Suspected unexpected serious adverse reactions (SUSAR)

## a) Definition:

ARs are all untoward and unintended responses to an investigational product related to any dose administered.

Unexpected ARs are suspected unexpected serious adverse reactions (SUSARs) if the following three conditions are met:

- the event must be serious (see section 9.2.2);
- there must be a certain degree of probability that the event is a harmful and an undesirable reaction to the medicinal product under investigation, regardless of the administered dose;
- the AR must be unexpected, that is to say, the nature and severity of the AR are not in agreement with the product information as recorded in the SmPC for an authorised medicinal product.

## 13.3 Adverse events, serious adverse events and suspected unexpected serious adverse reactions: Procedures

#### 13.3.1. Procedures for Recording Adverse Events:

For the first 7 days after immunisation at visits 1, 3 and 6 (Day 0 to Day 7), all AEs observed by the study team or reported by the participant's parent/ legal guardian, whether or not attributed to study medication, will be recorded in the RedCap or paper diary. Reactions occurring in the first 7 days after immunisation (including day of immunisation) will be divided up into: solicited reactions, which will be considered related to study vaccine unless stated otherwise; and unsolicited adverse events, which will be assessed for relatedness and graded for severity by a medically qualified member of the study team. There will be space in the electronic or paper diary to record the end date of adverse events that continue beyond Day 7. The RedCap system will allow review by clinical staff of grade 3 AEs in real-time.

Medical events not considered SAEs that occur 7 days after immunisation do not need to be recorded. Because of the possibility that medication may interfere with the evolution of an immune response, the details of any prescription medication that is given within 28 days following the 2, 4 or 12 month vaccinations will be recorded on the eDiary or paper diary. Information on paracetamol/ ibuprofen use within 72 hours prior to immunisation and in the 7 days following immunisation will be specifically asked for.

AEs will be recorded using the following guidance:

• Pre-existing medical conditions (present before start of the AE collection period) are considered "concurrent medical conditions" and should not be recorded as AEs. However, if the participant experiences a worsening or complication of such a condition, the

worsening or complication should be recorded as an AE. Investigators should ensure that the AE term recorded captures the change in the condition (e.g. "worsening of")

 Each AE should be recorded to represent a single diagnosis. Accompanying signs or symptoms (including abnormal laboratory values) should not be recorded as additional AEs.

All AEs that are considered related and result in a participant's withdrawal from the study or are present at the end of the study should be followed up until the end of symptoms or the condition becomes stable.

It will be left to the investigator's clinical judgment whether or not an AE is of sufficient severity to require the participant's removal from the study. A parent/ legal guardian may also voluntarily withdraw their child due to what he or she perceives as an intolerable AE.

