## 9.5.2 Visit 2: 7 days after V1 (range 7-14 days)

1. Check inclusion and exclusion criteria if still valid

2. Review eDiary or paper diary for AEs/SAEs since last visit

3. Record and report AEs/SAEs that occurred since last visit

4. Record paracetamol and/or ibuprofen use in 72h prior to immunisation.

5. Measure and record the participant axillary temperature

6. Administer 0.5ml dose of 4CMenB by intra-muscular injection into the left antero-lateral thigh, record site and time of vaccination and batch number in source document and in red book

7. After explanation according to JCVI recommendations, parents would be advised to give 2.5 mls of paracetamol (120mg/5ml) orally immediately after vaccination, and 2 other doses 4-6hours apart after last dose.

8. Observe the participant for 15 minutes after vaccination for any significant acute reactions, with appropriate medical treatment readily available in case of anaphylactic reaction. Any AEs occurring during the observation period should be recorded in the source document

9. Instruct parent/legal guardians to contact the study team immediately should they manifest any signs/ symptoms they perceive as serious or if the child is admitted overnight to hospital.

10. Leave with parents/guardians anaesthetic cream (unless spray to be used), dressing pads and instructions for blood test visit if not given previously

11. Schedule next visit

12. Study staff complete red book, paperwork in the case of no direct data entry and enter onto database

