## 9.5.3 Visit 3: 56 days post V1 (+14 days)

1. Check Inclusion/ exclusion criteria are still valid

2. Review eDiary or paper diary for AEs/SAEs and prescription medicine since the last visit

3. Record and report any AEs/SAEs that have occurred since the last visit.

4. Issue new eDiary or paper diary and remind parents to measure and record temperature, local and systemic reactions, AEs (for 7 days post any vaccination) and concomitant medications (for 28 days post vaccination).

5. Measure and record axillary temperature

6. Administer 0.5ml DTaP-IPV-Hib-Hep B by intra-muscular injection into the upper right anterolateral thigh (aP group), record in source document and in red book

7. Administer 0.5ml DTwP-Hib-Hep B by intra-muscular injection into the upper right antero-lateral thigh (wP group), record in source document and in red book

8. Administer 0.5ml PCV by intra-muscular injection into the upper left antero-lateral thigh record in source document and in red book

9. Administer 0.5ml IPV by intra-muscular injection into the lower left antero-lateral thigh (wP aroup), record in source document and in red book

10. Administer Rotavirus vaccine oral drops

11. Issue the parents/ legal guardian with a continuous temperature-monitoring device, together with instructions. Fit on the child and demonstrate how to fit, check function

12. Check parent familiar with how to measure and record temperature, local and systemic reactions, AEs (for 7 days post any vaccination) and concomitant medications (for 28 days post vaccination).

13. Observe the participant for 15 minutes after vaccination for any significant acute reactions, with appropriate medical treatment readily available in case of anaphylactic reaction. Any AEs occurring during the observation period should be recorded in the source document

14. Issue (only if parent's do not have any) and provide instructions on the use of paracetamol prophylaxis to those whose infant is randomised to receive wP

15. Instruct parent/legal guardians to contact the study team immediately should they manifest any signs/ symptoms they perceive as serious or if the child is admitted to the hospital.

16. Leave with parents/guardians anaesthetic cream (unless spray to be used), dressing pads and instructions for blood test visit if not given previously.

17. Schedule next visit

18. Study staff complete red book, paperwork in case of no direct data entry and enter onto database

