#### 9.11 Potential risks for participants and mitigation strategies

1) **Immunisation schedule:** In this study we will be changing the times of the primary immunisations, for a different schedule when compared with the UK routine schedule. Currently the UK primary immunisation schedule is at 2, 3 and 4 months of age, and in this study it will be at 2 and 4 months. This schedule change, only affects the timing of administration for a few of the immunisations, **but the number of total doses administered will not change**. The pertussis vaccine, will be discussed separately in the next section.

The vaccines that would have variations from the routine schedule are:

- Rotavirus vaccine (rotarix®): currently given in the UK at 2 and 3 months of age. In our study it would be given at 2 and 4 months of age. This schedule remains in the recommended timelines [58], i.e. the first dose provided after 6 weeks of age and last dose before 6 months of age. The study schedule is similar to other European countries and we do not anticipate that this alteration would have any negative impact on the study population.

- Meningitis B vaccine (Bexsero®): This vaccine is going to be administered at the recommended ages according to the UK routine schedule (2 and 4 months). A small variation compared with the routine procedures will occur. The vaccine will be given separately at 7-14 days after the 2 and 4 month immunisations. The main reason for this slight variation is that the Meningitis B vaccine is considered very reactogenic and in order to better assess possible side effects/reactogenecity of the study vaccine, we think it is preferable to separate the administration of those 2 vaccines. We do not anticipate that this change would have any negative impact since children are normally vaccinated in the routine schedule in a time frame of 2 weeks, from the first day that they are eligible.

- Pneumococcal vaccine, PCV (Prevenar13®): the UK schedule is changing during early 2020 from that used in the current study, 2 and 4 months and booster at 12 months (2+1) to a single dose of PCV to be given at 3 months followed by the booster dose at 12 months (1+1 schedule). Given this is the first 1+1 schedule to be used globally and the current study has no visits at 3 months the

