#### 13.4 Follow-up of adverse events

All AEs will be followed until they have abated, or until a stable situation has been reached. Depending on the event, follow up may require additional tests or medical procedures as indicated, and/or referral to the general physician or a medical specialist. SAEs need to be reported until the end of the study, as defined in the protocol.

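### Section 13.3.1 puts Day 7 both inside and outside the reaction window, and Day 7 is the nominal MenB day, so same-day MenB symptoms can enter the study-vaccine reactogenicity counts; the AE collection rules also conflict

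*Protocol*

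**What the plan says.** Section 13.3.1 sets the collection period with "For the first 7 days after immunisation at visits 1, 3 and 6 (Day 0 to Day 7), all AEs" and also provides for end dates of events that outlast Day 7. Two sentences on, it classifies events with "Reactions occurring in the first 7 days after immunisation (including day of immunisation) will be divided up into", which on a plain count is Day 0 to Day 6. It then says "Medical events not considered SAEs that occur 7 days after immunisation do not need to be recorded", which read literally puts Day 7 outside. The default attribution is "solicited reactions, which will be considered related to study vaccine unless stated otherwise".

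MenB is scheduled as "Visit 2: 7 days after V1 (range 7-14 days", and V4 has the same timing after V3 (sections 9.5.2 and 9.5.4, Table 1). Section 9.11 explains the gap: "in order to better assess possible side effects/reactogenecity of the study vaccine, we think it is preferable to separate the administration" of the two vaccines.

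Three rules govern non-serious AEs:
- Sections 9.8 and 13.3.1 limit collection to 7 days after V1, V3 and V6.
- The parent instructions at V1, V3 and V6 (sections 9.5.1, 9.5.3 and 9.5.6) extend AE recording to 7 days after any vaccination.
- The visit steps from V2 to V7 have no time limit; at V3 the step is "Record and report any AEs/SAEs that have occurred since the last visit".

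Secondary endpoint 9 counts infants with solicited and unsolicited symptoms after the 2, 4 and 12 month doses. It states no window.

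**The concern.** The one day on which the two windows differ is the target day for MenB, a vaccine that section 9.11 itself describes as very reactogenic. If Day 7 belongs to the window, a fever or irritability entered that evening goes into the V1 or V3 record and is presumed related to the pertussis vaccine. That works against the reason given for giving MenB separately.

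Endpoint 9 also includes unsolicited symptoms. Their count depends on whether staff follow the 7-day limit, the any-vaccination instruction or the open-ended visit step.

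**Working it through.** The protocol gives no figure to reproduce on this point. The check is a comparison of calendar days, followed by algebra for the direction of the effect.

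**1. Window against MenB day**

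| MenB given on | Overlap with Day 0-7 | Overlap with Day 0-6 |
|---|---|---|
| Day 7 | Day 7 (one day) | none |
| Days 8 to 14 | none | none |

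The overlap is at most 1 of 8 days, and only after V1 and V3. After V6 the next vaccines come at V7, 28 to 42 days later, so the V6 window is clear.

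**2. Which entries are exposed**

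At V2 and V4, diary review and AE recording (items 2 and 3) come before the injection (item 6), so only entries made later that day are at risk. No new diary is issued at V2 or V4. MenB goes into the left thigh and DTaP or DTwP into the right, so local reactions to the pertussis vaccine can be told apart by side. PCV and, in the wP arm, IPV share the left thigh with MenB. Systemic symptoms and axillary temperatures have no site, so they are the main exposure. Continuous temperature monitoring covers only 24 hours and is unaffected.

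**3. Direction of the effect**

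Let p be the true proportion with any symptom in the window. Let s be the share of infants given MenB on exactly day 7, and q the probability that MenB causes a symptom recorded later that day. If MenB symptoms are independent of earlier ones:

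observed proportion = p + (1 - p) × q × s

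observed difference = (p_wP - p_aP) × (1 - q × s)

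Both arms rise and the difference shrinks. The document gives neither q nor s. To show how far the answer depends on them, assume true proportions of 50% (aP) and 70% (wP):

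| q | s | aP | wP | Difference (points) |
|---|---|---|---|---|
| any | 0 | 50.0% | 70.0% | 20 |
| 0.5 | 0.5 | 62.5% | 77.5% | 15 |
| 0.8 | 1 | 90.0% | 94.0% | 4 |

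Every input in this table is an assumption. The table shows direction and is not an estimate.

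**4. Length of the AE collection periods**

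- Section 13.3.1: at most 8 days per study dose.
- Any-vaccination instruction: MenB on day 7 to 14, plus 7 days, reaches day 14 to 21 after V1 or V3.
- Visit steps: V2 to V3 spans 56 - 14 = 42 days to 70 - 7 = 63 days; V4 to V5 spans 28 to 42 days; V5 to V6 is about 7 months (5 to 12 months of age).

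The three rules give different sets of non-serious events for the same infant.

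**The case against.** The strongest reply is that the problem is narrow and partly guarded against. It needs MenB on exactly day 7 and an entry made after the injection, and the Day 0 to Day 6 wording in the same paragraph removes it. Relatedness can be overridden, and a medically qualified team member assesses unsolicited events. Days 0 to 6 are free of MenB for every infant, and section 9.11 calls wP symptoms short lived. All of this stands, and it limits the size. It does not remove the contradiction, because the protocol does not say which window governs and gives no rule for overriding the default attribution.

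On AE collection, it can be said that the 7-day limit is permissive, so recording more is untidy rather than forbidden, and that the SAP may define the endpoint 9 tables. That is fair, but the protocol still gives staff and parents instructions that do not agree.

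Three stronger readings are tempting and are not supported:
- A reader might infer that MenB reactions are generally counted against the study vaccine and that the separation of the two vaccines has failed. The overlap is one conditional day.
- A reader might infer selective recording by unblinded staff. The visit steps are the same for every infant in both arms.
- A reader might infer conflicting SAE end dates, since section 13.4 says "SAEs need to be reported until the end of the study, as defined in the protocol" and section 13.3.2 stops at the last visit. Section 13.3.2 concerns SAEs that occur up to that visit, while section 13.4 concerns follow-up, so the two are compatible.

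**Conclusion.** The point holds as an internal contradiction with a limited consequence. Under the Day 0 to Day 7 reading, systemic symptoms and temperatures entered after a day-7 MenB injection can be attributed by default to the study vaccine after V1 and V3. This raises the proportions in both arms and dilutes the aP-wP difference in secondary endpoint 9. It does not favour one arm by design. That direction assumes MenB symptoms are independent of earlier ones and that the table counts any symptom in the window; a per-symptom table would need a per-symptom q. No loss can be quoted, because the document gives neither the share vaccinated on day 7 nor a MenB reaction rate. The primary endpoint and the V6 data are not affected.

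The conflict between the three collection rules for non-serious AEs is also genuine and bears on the unsolicited part of endpoint 9.

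**What to change.** For endpoint 9 after V1 and V3, fix the window as Day 0 to Day 6, or exclude diary entries made after the recorded time of the MenB injection. The visit steps at V2 and V4 already require that time to be recorded. If diary entries carry no time of day, use Day 0 to Day 6. V6 needs no truncation for this reason.

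Either rule can be applied at analysis to data already collected. That matters because version 4.1 is dated 08-Dec-2023 and the study period ends in June 2024. V3 (4 months) precedes V7 (13 months) by about nine months, so an infant completing V7 by June 2024 had V3 by about September 2023, and new diary wording would come too late.

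State one collection rule for non-serious AEs and align sections 9.5.1 to 9.5.7, 9.8 and 13.3.1 with it. Restrict the endpoint 9 unsolicited counts to the single post-dose window, and list any non-serious events recorded outside it separately.

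The cost is wording and, at most, one diary day after each of V1 and V3. No visit or vaccination procedure changes.
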